#### 14.6.4. Safety

##### 14.6.4.1. CV Safety Endpoints

CV Safety Endpoints
Dates for Investigator Reported CV Safety Endpoints

 
All-cause hospitalization: admission date
 
All-cause hospital re-admission: admission date within 30 days following a discharge date
 
Death: date of death from the Death eCRF page
 

CONFIDENTIAL

204837

**CV Safety Endpoints**

- Myocardial infarction: date of onset of Myocardial Infarction/Unstable Angina symptoms from the MI/UA eCRF page
- Stroke: start date of neurological symptoms from the Stroke/TIA eCRF page
- Hospitalization for HF: Earliest of (ER admission date, Hospital admission date) from Heart Failure eCRF page
- Thromboembolic event: date of onset of thromboembolic event from the Thromboembolic Event eCRF page

**Dates for Adjudicated CV Safety Endpoints**

- Death: event date reported by CEC
- Myocardial infarction: event date reported by CEC
  - Fatal MI events only identified through a primary cause of death, without a corresponding positively adjudicated MI event: death event date reported by CEC
- Stroke: event date reported by CEC
  - Fatal stroke events only identified through a primary cause of death, without a corresponding positively adjudicated stroke event: death event date reported by CEC
- Hospitalization for HF: event date reported by CEC
  - Fatal heart failure/cardiogenic shock events only identified through a primary cause of death, without a corresponding heart failure event: death event date reported by CEC
- Thromboembolic event (DVT, PE, VAT): event date reported by CEC
  - Fatal PE events only identified through a primary cause of death, without a corresponding positively adjudicated PE event: death event date reported by CEC

Due to the design of the CRF, a fatal MI is reported as both an MI and a death. Both of these events will go through the adjudication process. It is possible that the MI could be negatively adjudicated, while the death is positively adjudicated with a primary cause of acute MI. The rationale for this is that the definition of a positively adjudicated MI (contained in the CEC charter) is more explicit than the definition of acute MI as a primary cause of death. Therefore, in analyses that include MI events without including all-cause mortality, the primary approach will be to include only those fatal MI events that correspond to a positively adjudicated MI event. These analyses will then be repeated for supportive purposes using all fatal MI events – including those fatal MI events only identified through a primary cause of death (i.e., acute MI) without a corresponding positively adjudicated MI event.

Additionally, a fatal MI event could have an event date that differs from the death date because the subject may have died as a result of the MI but not on the same day. For analysis of first occurrence MACE, MI or any other composite endpoint that includes both MI and death, if both the MI and death events are positively adjudicated, the MI date will be used as the event date. For analysis of CV mortality only and all-cause mortality only, the death date will be used.

Similarly, fatal stroke events are reported as both a stroke and a death. In analyses that include stroke events without including all-cause mortality, the primary approach will be to include only those fatal stroke events that correspond to a positively adjudicated stroke event. These analyses will be repeated for supportive purposes using all fatal stroke events – including those fatal stroke events only identified through a primary cause of death (i.e., stroke) without a corresponding positively adjudicated stroke event. For analysis of first occurrence MACE, stroke, or any other composite endpoint that includes stroke and death, if both the stroke and death events are positively adjudicated, the stroke date will be used as the event date. For analysis of CV mortality only and all-cause mortality, the death date will be used.

**CV Safety Endpoints**

Fatal heart failure events are reported as both a heart failure and a death. In analyses that include hospitalization for heart failure events without including all-cause mortality, a single approach which includes only those fatal hospitalization for heart failure events that correspond to a positively adjudicated hospitalization for heart failure event will be used. The definition of the hospitalization for heart failure endpoint includes requirements around hospitalization which are not captured in the associated primary cause of death (heart failure/cardiogenic shock), so identification of hospitalization for heart failure events through only a primary cause of death is not possible. However, supportive analyses of the hospitalization for heart failure endpoint may include all heart failure events. These supportive analyses would then be able to include fatal heart failure events from the death page (i.e. primary cause of death = heart failure/cardiogenic shock) that do not correspond to a positively adjudicated heart failure event. For analysis of hospitalization for heart failure or any composite endpoint that includes hospitalization for heart failure and death, if both the hospitalization for heart failure and death events are positively adjudicated, the hospitalization for heart failure date will be used as the event date. For analysis of CV mortality only and all-cause mortality, the death date will be used.

Fatal pulmonary embolism events are reported as both a pulmonary embolism and a death. In analyses that include pulmonary embolism events (i.e., thromboembolic events) without including all-cause mortality, the primary approach will be to include only those fatal pulmonary embolism events that correspond to a positively adjudicated pulmonary embolism event. These analyses may be repeated for supportive purposes using all pulmonary embolism events – including those fatal pulmonary embolism events only identified through a primary cause of death (i.e., pulmonary embolism) without a corresponding positively adjudicated pulmonary embolism event. For analysis of pulmonary embolism or any composite endpoint that includes pulmonary embolism and death, if both the pulmonary embolism and death events are positively adjudicated, the pulmonary embolism date will be used as the event date. For analysis of CV mortality only and all-cause mortality, the death date will be used.

In the situation that there is a fatal MI (or fatal stroke, hospitalization for heart failure, or pulmonary embolism) that does not have both an MI (or stroke, hospitalization for heart failure, or pulmonary embolism) endpoint and a death endpoint reported, the date of the event that is reported will be used in the analysis of all relevant endpoints. This would additionally apply to situations where the MI (or stroke, hospitalization for heart failure, or pulmonary embolism) may occur within an analysis period and the death may occur outside of the analysis period; the endpoint with the date in the analysis period will be used for all relevant endpoints.

**Missing or Partial Endpoint Dates**

- If event dates are missing or partial and there is not sufficient information to classify the time period of the event, the event will be classified as occurring on-treatment and post-randomization. The event will also be considered to have occurred during the follow-up for cardiovascular events as defined in Section 14.6.4.
- The following rules for missing or partial event dates for events other than death will be implemented as long as the imputed date is after the randomization date. If the imputed date is prior to the randomization date, then the date of randomization will be imputed for the event date.
  - If only the day of the month is missing, impute the first day of the month (e.g., --FEB2016 would impute as 01FEB2016)
  - If the month and day of the month are missing, impute 01JAN (e.g., ----2016 would impute as 01JAN2016)
  - If the year, month, and day of month are missing, impute the randomization date
- The following rules for missing or partial death dates will be implemented as long as the imputed date is after the randomization date. If the imputed date is prior to the randomization date, then the date of randomization will be imputed for the death date.
  - The latest clinic visit, telephone visit, other contact with subject visit, CV endpoint (other than death), AE or SAE date, or date last known to be alive will be determined. If the year,

CONFIDENTIAL

204837

CV Safety Endpoints

month, and day of month of the death are missing then the death date will be imputed as the latest of the dates.
 
 
○ If only the day of the month of death is missing, then impute the first day of the month (e.g., --FEB2016 would impute as 01FEB2016). However, if this imputed date results in a date that is prior to the latest clinic visit, telephone visit, other contact with subject visit, CV endpoint (other than death), AE or SAE date, or date last known to be alive then impute the missing day of death as equal to this date instead. For example: 
 
▪ If --FEB2016 is given as the death date and there is a non-fatal MI on 08FEB2016, then the imputed date of death would be 08FEB2016 rather than 01FEB2016 such that the death is not before the non-fatal MI.
 
▪ If --MAR2016 is given as the death date and the latest date is a non-fatal MI on 08FEB2016 then the imputed date of death would be 01MAR2016.
 
 
 
○ If the month and day of the month of death are missing, then impute as 01JAN (e.g., ----2016 would impute as 01JAN2016). However, if this imputed date results in a date that is prior to the latest clinic visit, telephone visit, other contact with subject visit, CV endpoint (other than death), AE or SAE date, or date last known to be alive then impute the missing month and day of death as equal to this date instead. For example: 
 
▪ If ----2016 is given as the death date and the latest date is a non-fatal MI on 08FEB2016 then the imputed date of death would be 08FEB2016 rather than 01JAN2016 such that the death is not before the non-fatal MI.
 
▪ If ----2017 is given as the death date and the latest date is a non-fatal MI on 08FEB2016 then the imputed date of death would be 01JAN2017.
 
 
 
○ For deaths that occur after subjects have prematurely withdrawn from the study, missing or partial dates will be imputed as specified above except if the imputation places the death prior to or on the premature withdrawal date. In this case the death date will be imputed as the premature withdrawal date + 1 day.
 

Order of CV Safety Endpoint Events

 
• If multiple events occur on the same day or have imputed dates that place them on the same day, but it is not clear which event occurred first, then the following order will be applied: 
 
1. MI
 
2. Stroke
 
3. Hospitalization for Heart Failure
 
4. Thromboembolic Event: DVT
 
5. Thromboembolic Event: VAT
 
6. Thromboembolic Event: PE
 
7. Death
 
 
 

CV Mortality

 
• CV mortality includes all deaths indicated as having a cardiovascular primary cause of death (including fatal MI and fatal stroke events) as well as deaths with an undetermined primary cause of death that are indicated to be either presumed sudden death or presumed cardiovascular death. Deaths with an undetermined primary cause of death that are indicated to be an unknown death will not be included as a CV mortality event.
 

Heart Failure Events

 
• The primary heart failure event of interest in this study is hospitalization for heart failure. However, investigators are requested to report all potential heart failure events for adjudication, even if there was no hospitalization associated with the event.
 
• The CEC will categorize heart failure events into one of the following adjudicated event types: 
 
○ Hospitalization for Heart Failure
 
 
 

CONFIDENTIAL

204837

CV Safety Endpoints	

 
○ Urgent ER/ED Visit for Heart Failure
 
○ Urgent Office/Practice Visit for Heart Failure
 
○ Negative adjudication (i.e., not one of the heart failure events above)
 
● For purposes of endpoints that contain hospitalization for heart failure as a component, only the events adjudicated by the CEC as Hospitalization for Heart Failure will be included.
 
	
Investigator-reported Endpoint Events for Concordance	

 
● For purposes of concordance tables, events with an investigator-reported event date <math>\geq</math> randomization date during the time period for follow-up of cardiovascular events, that meet the following final diagnosis criteria will be considered to be investigator-reported endpoint events:
 
	
Endpoint	Investigator-reported final diagnosis (from eCRF)
Myocardial infarction	Myocardial infarction
Stroke	Primary ischemic stroke (with or without hemorrhagic transformation), Primary intracranial hemorrhage, Retinal/ocular hemorrhage or infarction, Unknown type of stroke
Hospitalization for Heart Failure	
Systolic heart failure, Diastolic heart failure, Heart failure - unspecified type
 
Additional criteria:  If admission/discharge times are non-missing, at least one of the following must be true (1-3):
 
 
1. Time in hospital is <math>\geq 24</math> hours
 
2. Time in ED/ER is <math>\geq 24</math> hours
 
3. Consecutive time in hospital + time in ED/ER is <math>\geq 24</math> hours
 
 
Or if admission/discharge times are missing, then at least one of the following must be true (4-6):
 
 
4. Change in calendar date between hospital admission and discharge
 
5. Change in calendar date between ED/ER admission and discharge
 
6. Change in calendar date between consecutive hospital and ED/ER admission and discharge
 

Thromboembolic Event (DVT, PE, VAT)	Deep Vein Thrombosis (DVT), Pulmonary Embolism (PE), Vascular Access Thrombosis
All-cause mortality	Any death record
CV mortality	Any Cardiovascular primary cause of death
Non-CV mortality	Any Non-Cardiovascular primary cause of death
Unknown (sub-category of All-cause mortality)	Any Unknown primary cause of death

Events with an adjudication record, but without an investigator reported record, will also be included in the concordance summaries
	
All-cause Hospitalization	

 
● All-cause hospitalization events are defined to be hospital admissions recorded on the Hospitalization eCRF form with a hospitalization duration <math>\geq 24</math> hours.
 
● Hospitalization rate (per year) across the study = number of all-cause hospitalization events / [follow-up time (days) / 365.25].
 
	
General Definitions	

 
● Time to event (days) = date of event – randomization date + 1
 
● Censored time (days) = censoring date – randomization date + 1
 
	

**CV Safety Endpoints**

- First event person years = (cumulative total time to first event for subjects who have the event + cumulative total of censoring time for subjects without the event) / 365.25
- First event incidence rate (per 100 person years) = (100 \* number of subjects with at least 1 event) / first event person years
- First event absolute rate difference (per 100 person years) = daprodustat incidence rate (per 100 person years) – rhEPO incidence rate (per 100 person years)

**Evaluation Time Periods for CV Endpoints****Time Period for Follow-up of Cardiovascular Endpoints**

The period for capturing CV safety endpoints begins at randomization. The end of this time period is the date of study completion/withdrawal, with the exception that if a death has been reported in the clinical database after this time, then the death will be included in the analysis.

Any endpoints that occurred before the start of this time period are considered to be prior to the time period for follow-up of cardiovascular safety events, and any endpoints that occurred after the end of this time period are considered to be post the time period for follow-up of cardiovascular safety endpoints.

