8.2.1. Withdrawal of Consent for Contact

Specific wording is included in the informed consent form which permits participants to discontinue study treatment and study procedures, but states an expectation that follow-up information will always be required. Participants will agree to this at the time of consenting.

Withdrawal of consent from the study is expected to be a rare occurrence. If a participant expresses a wish to withdraw consent from the study, the investigator will review the following contact options with the participant:

- In-clinic and phone visits
- Follow-up via medical records review and/or other treating physician
- Follow-up via family member or other third party contact

If all of these options are refused, then no further study visits or study-related telephone contacts will be conducted and the participant will be considered to have withdrawn consent. The investigator will be required to document that all alternative options have been reviewed with the participant.

For these participants, information regarding vital status will continue to be collected from available sources including those in the public domain based on accepted local laws and regulations. Where permitted, a third party may be used to obtain information.

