**Time Period for Vital Status**

The period for capturing vital status begins at the date of randomization. The end of this time period is defined as follows:

- For all subjects known to have died, use the date of death
- For all subjects who complete the study, use the study completion date (see Section 14.6.1)
- For all subjects who withdraw from the study, but vital status has been ascertained, *and are known to have not died* – use the latest date last known to be alive. If vital status has not been ascertained following study withdrawal, use the study withdrawal date

Any endpoints that occurred before the start of this time period are considered to be prior to the time period for vital status, and any endpoints that occurred after the end of this time period are considered to be post the time period for vital status.

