## CONFIDENTIAL

204837

Safety: Tables					
No.	Population	IDSL / Example Shell	Title	Programming Notes	Deliverable [Priority]
3.012	All Randomized (ITT)	SAFE_T17	Summary of Analysis of Change from Baseline to Week 52 in Post-Randomization Blood Pressure Parameters Including the Stabilization Period	MMRM On- and off-treatment BP values Per RAP Section 8.1 the post-dialysis BP values will be used.	SAC
3.013	All Randomized (ITT)	SAFE_T18	Summary of Analysis of Change from Baseline to End of Treatment in On-Treatment Blood Pressure Parameters	ANCOVA Per RAP Section 8.1 the post-dialysis BP values will be used.	SAC
3.014	All Randomized (ITT)	SAFE_T19	Summary of Analysis of On-Treatment Blood Pressure Exacerbation Events	Based on post-dialysis BP	SAC
3.015	All Randomized (ITT)	SAFE_T21	Summary of On-Treatment Blood Pressure Exacerbation Event		SAC
Exploratory Cardiovascular Safety Analyses					
3.016	All Randomized (ITT)	SAFE_T1	Summary of First Occurrence of Adjudicated MACE during the Time Period for Follow-up of Cardiovascular Events		SAC
3.017	All Randomized (ITT)	SAFE_T2aa	Summary of Analysis of First Occurrence of Adjudicated MACE during the Time Period for Follow-up of Cardiovascular Events		SAC
3.018	All Randomized (ITT)	SAFE_T3	Summary of All Adjudicated MACE during the Time Period for Follow-up of Cardiovascular Events		SAC

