**CONFIDENTIAL**

204837

Safety: Tables					
No.	Population	IDSL / Example Shell	Title	Programming Notes	Deliverable [Priority]
3.019	All Randomized (ITT)	SAFE_T1	Summary of First Occurrence of Adjudicated MACE or Thromboembolic Events during the Time Period for Follow-up of Cardiovascular Events		SAC
3.020	All Randomized (ITT)	SAFE_T2ba	Summary of Analysis of First Occurrence of Adjudicated MACE or Thromboembolic Events during the Time Period for Follow-up of Cardiovascular Events		SAC
3.021	All Randomized (ITT)	SAFE_T1	Summary of First Occurrence of Adjudicated MACE or Hospitalization for Heart Failure during the Time Period for Follow-up of Cardiovascular Events		SAC
3.022	All Randomized (ITT)	SAFE_T2ba	Summary of Analysis of First Occurrence of Adjudicated MACE or Hospitalization for Heart Failure during the Time Period for Follow-up of Cardiovascular Events		SAC
3.023	All Randomized (ITT)	SAFE_T1	Summary of First Occurrence of Adjudicated MACE or Thromboembolic Events or Hospitalization for CHF during the Time Period for Follow-up of Cardiovascular Events		SAC
3.024	All Randomized (ITT)	SAFE_T2ba	Summary of Analysis of First Occurrence of Adjudicated MACE or Thromboembolic Events or Hospitalization for CHF during the Time Period for Follow-up of Cardiovascular Events		SAC
3.025	All Randomized (ITT)	SAFE_T2ba	Summary of Analysis of Adjudicated All-Cause Mortality during the Time Period for Vital Status		SAC
3.026	All Randomized (ITT)	SAFE_T2ba	Summary of Analysis of Adjudicated CV Mortality during the Time Period for Follow-up of Cardiovascular Events		SAC
3.027	All Randomized (ITT)	SAFE_T2ba	Summary of Analysis of First Occurrence of Adjudicated Myocardial Infarction (Fatal and Non-Fatal) during the Time Period for Follow-up of Cardiovascular Events		SAC

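### Late deaths enter the MACE, CV-mortality and (for completers) all-cause mortality rates without comparable survivors' later person-time, a small upward bias

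*SAP*

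**What the plan says.** The general definitions in SAP 14.6.4.1 form first-event person-years from "cumulative total time to first event for subjects who have the event + cumulative total of censoring time for subjects without the event", in days divided by 365.25. The incidence rate is 100 times the number of subjects with an event, divided by that total.

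Two windows matter.

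- **Follow-up of cardiovascular endpoints.** "The end of this time period is the date of study completion/withdrawal", except that "if a death has been reported in the clinical database after this time, then the death will be included in the analysis". Other endpoints after that date fall outside the window. Table 3.017 ("Summary of Analysis of First Occurrence of Adjudicated MACE during the Time Period for Follow-up of Cardiovascular Events") and Table 3.026 ("Summary of Analysis of Adjudicated CV Mortality during the Time Period for Follow-up of Cardiovascular Events") use it, as do the composites containing death and the MACE Kaplan-Meier plot (Figure 3.005).
- **Vital status.** Only all-cause mortality uses this (Table 3.025). Deaths end at the death date. Withdrawn subjects known to be alive run to the last date known alive; those whose status was not ascertained stop at withdrawal. For the rest: "For all subjects who complete the study, use the study completion date".

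Protocol 8.2.1 says that after consent is withdrawn "information regarding vital status will continue to be collected from available sources".

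**The concern.** Follow-up length depends on the outcome. Take two participants who withdraw free of MACE on the same day, one of whom later dies. The one who dies is an event, followed to death; the one known to be alive is censored at withdrawal. Because MI and stroke stop at the window's end, parts of one composite are also observed over different periods. In all-cause mortality, completers have the same problem: a later death counts, but a surviving completer's later time does not.

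Rates, rate differences and the MACE Kaplan-Meier curve make up most of the trial's cardiovascular safety comparison (Protocol 10.3.2; SAP 8.2). Protocol section 3 also plans a separate safety analysis using the once-daily outcomes trial. In the Kaplan-Meier plot, once survivors are censored at completion, only future decedents remain at risk. If the longest time in an arm is such a death, the event-free estimate falls to zero.

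**Working it through.** **Inputs from the documents.** 402 randomized, 268 and 134 by arm (Protocol 10.1.1); 52 weeks of treatment; follow-up visit 4 to 6 weeks after last dose; fewer than 80 first MACE expected (Protocol 10.3.2).

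**Assumed, because the documents give no values.** Constant hazards: MACE 10, 15 or 20 per 100 person-years (PY), of which death 6, 9 or 12. Withdrawal of 2, 5 or 10%, spread evenly over the year, with every later death found up to Week 52. After completion, 25% or 100% of deaths found over 5 weeks.

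**The plan's own figure.** Fewer than 80 MACE cannot be derived. It gives only a ceiling: 80/402 = 19.9 per 100 randomized, or −ln(1 − 80/402)/(364/365.25) = 0.223, about 22 per 100 PY. The assumed rates lie below that.

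**Formula.** Planned rate = 100 × (E + d)/(P + p). E and P are events and PY inside the window, d the late deaths, and p the decedents' own time after the window. E/P returns the true rate. The ratio d/p is far higher, because p omits the survivors.

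**1. MACE, withdrawals.** Middle case, 10% withdrawal: E = 53.10, P = 353.98, rate 15.00. Late deaths d = 1.67, p = 0.55. Planned rate = 100 × 54.77/354.53 = 15.45, or +3.0%. Those 1.67 deaths arose from 18.50 PY, of which only 0.55 is counted.

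| True MACE rate | 2% withdraw | 5% | 10% |
|---|---|---|---|
| 10.00 | 10.06 | 10.15 | 10.30 |
| 15.00 | 15.09 | 15.22 | 15.45 |
| 20.00 | 20.11 | 20.28 | 20.58 |

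Adding all 18.50 PY to the MACE denominator does not repair this: 100 × 54.77/372.48 = 14.70, too low, because MI and stroke are not captured after withdrawal.

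**2. MACE, completers, 5 weeks.** Middle case, no withdrawals: E = 55.82, P = 372.12, and 346.2 complete MACE-free. Late deaths = 346.2 × (1 − exp(−0.09 × 5/52)) = 2.98. All reported: 100 × 58.80/372.26 = 15.80 (+5.3%). A quarter reported: 100 × 56.57/372.16 = 15.20 (+1.3%). Across the three hazards: +1.3 to +1.4% and +5.1 to +5.5%.

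**3. All-cause mortality.** For withdrawn participants with status ascertained, the vital-status rule returns the true 6.00, 9.00 and 12.00. For completers over 5 weeks, middle case: 34.49 deaths in 383.18 PY; 3.17 late deaths add 0.15 PY; 100 × 37.66/383.33 = 9.82 (+9%) if all are reported, and 9.21 (+2%) if a quarter are.

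**4. Difference between arms, equal true rates.** With 10% withdrawal on daprodustat and 3% on epoetin, the middle case gives 15.45 − 15.13 = 0.32 per 100 PY; the range is 0.22 to 0.41. A second set of assumptions (MACE 12 per 100 PY, 8 of them deaths; completers followed 1.08 years, withdrawers 0.5; status known for 7 months after withdrawal) gives 12.21 at 5% and 12.66 at 15%, a difference of 0.45.

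**5. Against the precision.** In that last case PY are about 268 × 0.936 = 251 and 134 × 0.987 = 132. SE = 100 × √(0.12/251 + 0.12/132) = 3.7 per 100 PY, so the 95% half-width is about 7.3. A shift of 0.45 is 0.12 SE.

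**The case against.** **The exception may cover only late paperwork.** The wording says reported, so it might mean deaths that occurred inside the window. That does not stand: the date-imputation rules in SAP 14.6.4.1 provide for deaths occurring after premature withdrawal, and the note to Figure 3.005 points to this exception.

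**The effect is small and the analysis descriptive.** This stands. Protocol 10.3.2 says the trial is not powered for formal CV analysis, and SAP 8.2 labels these analyses exploratory. Protocol 8.2.1 expects withdrawal of consent to be rare, and those who stop treatment stay in the study. No test or decision rule changes.

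**Dropping deaths after withdrawal has its own bias.** This also stands. Someone who withdraws while deteriorating and soon dies would vanish from a truncated MACE rate. Hence the fix shows both versions.

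**Consistency with the once-daily trial.** Its censoring rules are not in these documents, so whether a change here helps or harms comparability cannot be judged.

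**Stronger readings a reader might infer.** One is that every mortality rate lacks person-time to match its late deaths. The documents do not support that: a decedent's own time is counted, and all-cause mortality credits withdrawn participants to the last date known alive. Another is that inflation is much larger, 15% or more, as full capture of completers' deaths over 13 weeks or longer would give. No scheduled contact follows the follow-up visit, Protocol 9.2.1 does not oblige investigators to seek events in former participants, and the continued vital-status collection in Protocol 8.2.1 concerns those who withdraw consent.

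**Conclusion.** The point holds in limited form. For MACE, the death-containing composites and CV mortality, the window rule inflates rates in both arms after withdrawal and after completion. For all-cause mortality it does so for completers; among withdrawn participants, a gap remains only where survivors' status was not ascertained. The on-treatment CV window has no death exception and is unaffected.

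On the assumptions above, MACE inflation is roughly 0.6 to 3% from withdrawals and 1 to 5% from a 5-week post-completion window. The upper end of the latter becomes plausible if the completion date is the Week 52 visit, because adverse events are actively collected until the follow-up visit; Protocol 5.3 and SAP 14.6.1 do not say which visit supplies the date. A false difference of 0.2 to 0.45 per 100 PY needs withdrawal to differ by arm. None of this would change a conclusion alone, but the stated rule creates the bias and a few sentences remove it.

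**What to change.** - **All-cause mortality.** Set one cut-off from randomization (for example planned Week 52 plus follow-up) for both deaths and person-time. Censor every survivor, completers included, at the earlier of that cut-off and the latest date known alive.
- **MACE, composites and CV mortality.** State the event-free censoring date, which the SAP only implies. Report rates and the Kaplan-Meier curve with deaths ending at completion/withdrawal, as MI and stroke do. Add a supportive table that includes later deaths up to the common cut-off.
- **Definition.** Say whether the study completion date is the Week 52 visit or the follow-up visit.

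The cost is SAP wording and supportive output. A few late deaths move to the supportive table, and the truncated MACE rate may miss deaths after informative withdrawal, which is the reason for showing both.
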